If a dyad is assigned to the SPIRIT-remote group, a research assistant trained to handle technical aspects of Zoom will schedule a phone call to take the surrogate through the steps of using email to follow URL links that open Zoom. He/she will also guide the surrogate through practice in using basic videoconference operations, e.g., accepting an incoming conference invitation, viewing shared documents, muting/unmuting the microphone or camera, and ending the call. For dyads with a computer without video capabilities, a loaner web cam (and headset and microphone as needed) will be shipped as soon as the group assignment is known. This research assistant will initiate the Zoom call for SPIRIT-remote sessions and silently observe sessions to troubleshoot difficulties the dyad or interventionist might encounter. These procedures have been used effectively in the Tele-Savvy pilot and current R01 project. The interventionist will confirm a follow-up call for outcome assessment to occur in the next 2-3 days ideally.

Usual Care at the Emory ADC. At the time of the diagnosis of a dementing illness, an advanced practice nurse provides written information on advance directives to a patient and his/her family caregiver and reviews this information and encourages them to complete an advanced directive. This typically takes about 10 minutes. Patients and their family members may be referred to attorneys who can assist them in completing an advance directive. If completed, the presence of an advanced directive is documented in the electronic medical record and a copy of the advance directive is scanned to the electronic chart. Patients and families may be referred to a support group program organized by a social worker in which legal and financial issues are discussed in a group setting (by a lawyer). We will review the patient’s medical records at the clinic at baseline and quarterly to track activities associated with usual care. To capture any changes in usual care, policy and procedures related to ACP at the clinic will be reviewed every 6 months by a research assistant.

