- **Surrogate decision-making confidence** will be measured using the 5-item Decision Making Confidence (DMC) scale (Cronbach’s $\alpha = 0.81-0.90$ ^{28,58}); higher scores reflect greater comfort in performing as a surrogate (0=“not confident at all” to 4=“very confident”). DMC assesses a surrogate’s confidence in: knowing the patient’s wishes, ability to make treatment decisions even in a highly stressful situation, ability to seek information about risks and benefits of medical choices, ability to handle unwanted pressure from others, and ability to communicate with providers about the patient’s wishes.
- We will also assess the **overall preparedness for end-of-life decision making** using the investigator-developed measure. The measure assesses the level of preparedness for end-of-life decision making in the cognitive, emotional, and behavioral dimensions on a 4-point scale (4=strongly agree to 1=strongly disagree) with higher scores indicating higher levels of preparedness. Patient and surrogate each will complete this measure separately.

Completion of Advance Directives (at 12 months). A research assistant will review the patient’s medical record to determine if the patient has completed an advance directive (a medical power of attorney or living will) by 12 months. If there is no documentation, the research assistant will call the surrogate to confirm.

Surrogates’ Perceived Impact of SPIRIT (intervention group only). At 12 months, 44-46 surrogates will participate in a semi-structured interview by phone: approximately 26 surrogates of patients who have progressed to an advanced stage (CDR score > 1 ; 22% progression rate^{33,113-115}) and 20% randomly selected surrogates of patients who have not progressed (~18-20 surrogates). A research assistant will review medical records to identify if a patient’s dementia has progressed. A trained interviewer/research assistant will conduct the interview using the Perceived Impact Interview Guide, which includes questions about surrogates’ experiences with the treatment condition, the perceived impact of the treatment condition on their loved ones and themselves, and what they found most and least helpful and why. This 15-30 minute interview will be audio-recorded and transcribed.

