Descriptors and Potential Covariates (collected at baseline). Patients and surrogates will each complete a Sociodemographic Profile which includes demographic information and previous end-of-life decision-making experience. Patients’ clinical characteristics, (date of dementia diagnosis, CDR score, MoCA or MMSE scores, and comorbid conditions) will be abstracted from the patient’s medical records. For patients whom we do not have access to their medical records, study staff will gather a patient’s clinical characteristics from the surrogate. The Medical Profile at Enrollment and the Quarterly Medical Record Review will both require surrogate report when medical records are unavailable.

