9.4.3 ANALYSIS OF THE SECONDARY ENDPOINT(S)

SPIRIT effect on advance directive completion (secondary aim): This analysis will be limited to patients who did not have an advance directive at the time of enrollment. For this binary outcome (completed or not completed) measured post intervention, the probability of completion will be estimated for the three groups using logistic regression. Baseline characteristics that differ across groups will be adjusted. Adjusted group mean proportions of completion will be compared between the groups; adjustments for multiple comparisons will be made using Tukey's test.

Surrogates' perceived impact (secondary aim): As in our previous work,¹²⁶ qualitative analysis will use content and thematic techniques.¹²⁷ Initial coding involves line by line examination, labeling, and organizing of data into segments, preserving detail in participants' words.¹²⁸ To optimize validity, codes and definitions will be reviewed and refined by the research team and applied to subsequent interviews.¹²⁹ Related codes will be grouped into categories representing aspects of the surrogates' experiences. Similarities, differences, and trends across cases will be examined.¹³⁰ Then, data will be organized into themes. This work will be done by Drs. [name] and [name] and the project director; discrepancies will be resolved by consensus. To explore differences in themes by AD progression and by treatment condition, we will count the occurrence of themes ("quantitizing")^{131,132}; the occurrence of each theme will be counted only once for a participant even if it is mentioned more than once. The data will be graphed to facilitate pattern interpretation.¹³³

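### The 12-month advance-directive outcome can count directives signed before enrollment: no signing date is required, and a negative accessible chart is checked with the surrogate only at 12 months

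*Combined protocol and SAP*

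**What the plan says.** The outcome is defined in section 8.1 (Stage 1B, Completion of Advance Directives). A research assistant reviews the chart to see whether the patient "has completed an advance directive (a medical power of attorney or living will) by 12 months". If the chart shows nothing: "If there is no documentation, the research assistant will call the surrogate to confirm". No signing date is requested, and no rule separates directives made before enrollment from those made after it.

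The analysis set is defined in section 9.4.3: "This analysis will be limited to patients who did not have an advance directive at the time of enrollment". The source of that status is not named there or elsewhere.

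The nearest baseline procedures are these:

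- Section 6.1.1 has staff review "medical records at the clinic at baseline and quarterly to track activities associated with usual care", where the patient comes from a clinical setting.
- Section 8.1 (Descriptors and Potential Covariates) lists the clinical items: "date of dementia diagnosis, CDR score, MoCA or MMSE scores, and comorbid conditions) will be abstracted". It also describes a Sociodemographic Profile, "which includes demographic information and previous end-of-life decision-making experience". Neither description mentions directive status.
- The same paragraph covers patients whose charts cannot be reached: "The Medical Profile at Enrollment and the Quarterly Medical Record Review will both require surrogate report when medical records are unavailable".

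The exclusion criteria in section 5.2 do not screen for an existing directive, so patients who hold one can be enrolled.

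**The concern.** The aim is about directives that come into being after the intervention. Only the enrollment restriction in 9.4.3 keeps older directives out, so it works only if enrollment status is measured at least as thoroughly as the 12-month outcome. As written, it is not. At 12 months a negative chart is treated as inconclusive and the surrogate is called. At baseline, for a patient with an accessible chart, no such call is described. A patient whose directive was drawn up elsewhere and never scanned can move from absent to completed without signing anything new.

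The setting makes this plausible. Section 6.1.1 says families may be referred to attorneys. It describes filing a completed directive in the chart for the Emory ADC ("the presence of an advanced directive is documented in the electronic medical record") but states no such filing step for the other settings, and it reports no fixed advance care planning procedure at Emory Geriatrics or the Grady clinics.

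At stake is the only quantitative between-arm comparison at one year. If enrollment status is not collected properly, analysts cannot reconstruct it afterwards.

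**Working it through.** The plan gives no rate, sample size or power for this outcome, so there is no figure of its own to reproduce. The check compares the two ascertainments and then illustrates the size.

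**Ascertainment side by side**

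| | Enrollment | 12 months |
|---|---|---|
| Named source of directive status | None | Chart, then surrogate |
| Chart accessible but negative | No surrogate check described | Surrogate is called |
| Chart not accessible | Surrogate report, but directive status is not a listed item | Surrogate |
| Signing date | Not requested | Not requested |

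The mismatch is in the second row.

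**Illustration of size**

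Let u be the share of the analysis set that already holds an older directive, missed at enrollment and found at 12 months. Let p be the true rate of new completion in an arm. If u is the same in both arms:

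- observed rate = u + (1 − u)p
- observed risk difference = (1 − u) × true risk difference

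All values of u, and the pair 20% and 45%, are assumptions. The true odds ratio for that pair is (0.45/0.55)/(0.20/0.80) = 3.27.

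| u | Usual care | SPIRIT | Risk difference | OR |
|---|---|---|---|---|
| 0 | 20.0% | 45.0% | 25.0 points | 3.27 |
| 10% | 28.0% | 50.5% | 22.5 points | 2.62 |
| 20% | 36.0% | 56.0% | 20.0 points | 2.26 |
| 30% | 44.0% | 61.5% | 17.5 points | 2.03 |

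The second scenario uses the 39% completion figure from section 2.2 as the usual-care rate and the same assumed 25-point difference, so 64% under SPIRIT. The odds ratio is 2.78 at u = 0, then 2.54, 2.36 and 2.21 at u = 10%, 20% and 30%. The risk differences are the same as in the table.

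For power, assume 37 analysed patients per arm. This is 61% of 60, as if 39% already held a directive and half of the 120 dyads were in each arm. A two-sided 5% comparison of 39% and 64% has power 0.58 at u = 0, 0.50 at 10%, 0.42 at 20% and 0.35 at 30%.

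**Does a date rule alone repair it?**

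No. If patients with older directives stay in the set and are recoded as non-completers, the observed rate is (1 − u)p. At u = 20% with 20% and 45%, that is 16% against 36%. The risk difference is still 20 points, and the OR is (0.36/0.64)/(0.16/0.84) = 2.95, not 3.27. These patients have to leave the analysis set.

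**The case against.** The best defence is that 9.4.3 presupposes a recorded enrollment status. The case forms are not in the documents, and the description of the Sociodemographic Profile need not be exhaustive. Some clinics ask about directives (Georgia Memory Net, Rush), and the Emory ADC files completed ones. Quarterly chart reviews would show roughly when a directive appeared. For a patient without a directive at enrollment, completed by 12 months reads most naturally as completed since enrollment, and the caller is free to ask when.

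These points reduce the likely size but do not close the gap. The clinic inquiries are described as usual care, not as the trial's baseline measure. A quarterly review dates the chart entry, not the signature. Asking for the date is possible but not required.

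Four stronger readings are tempting and are not supported:

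- A reader might infer that enrollment status rests on the chart alone. Sections 6.1.1 and 8.1 provide surrogate report when records are unavailable, so settings that keep no health records are not the weak spot. The gap concerns patients with accessible charts.
- A reader might infer that old directives will be counted as new. The plan leaves room for this but does not prescribe it.
- A reader might infer a bias in SPIRIT's favour because the session encourages a power of attorney. That passage of 6.1.1 describes SPIRIT before modification, and only surrogates outside the usual family order. SPIRIT could still lead families to find or file old papers, but nothing in the documents shows it.
- A reader might infer that directives are usually made outside the clinic. Section 6.1.1 says only that referral to attorneys may occur.

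**Conclusion.** The point holds in this form: enrollment status has no named source, a negative accessible chart is followed up with the surrogate at 12 months but not, as far as described, at baseline, and no signing date is required. Directives that predate enrollment can therefore enter the outcome as completions.

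Under equal misclassification across arms, the risk difference shrinks by the factor 1 − u. With 20% against 45%, the OR goes from 3.27 to 2.62 at u = 10% and 2.26 at u = 20%. Both the rates and u are assumed, so the actual size is unknown and may be small. If detection of old directives differs by arm, the bias could go either way.

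The change should be made, but it is not critical. The outcome is secondary in sections 1.1 and 9.4.3 and exploratory in sections 2.2 and 3. No sample size rests on it, and no primary-endpoint figure changes.

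**What to change.** In sections 8.1 and 9.4.3:

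1. At the baseline call, ask every surrogate the same directive question that is used at 12 months. Define no directive at enrollment as negative on both that answer and the chart, where there is one.
2. At 12 months, record the signing date of every directive in both arms, whether found in the chart or reported by the surrogate. Count as completions only directives signed after randomization. Remove patients whose directive predates enrollment from the analysis set; do not code them as non-completers. State how a directive signed between enrollment and randomization is handled.

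For dyads already enrolled, step 1 is no longer possible, so apply step 2 to all of them. The present 12-month call is made only when the chart is negative and would give no date for directives found in the chart.

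The cost is one question on an existing call and one date field, with an extra contact where the chart copy gives no date. Some dates will be approximate, so the plan should say how undatable directives are treated. The analysed subset becomes slightly smaller.

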3 OBJECTIVES AND ENDPOINTS

OBJECTIVES	ENDPOINTS	JUSTIFICATION FOR ENDPOINTS
Aim 1		
Adapt SPIRIT (in person) to target patients with mild AD and their surrogates through a process of modification-pretesting-refinement using stakeholders (patients, family caregivers, and clinicians) and experts, including adapting the delivery mode to interactive web-based videoconferencing (SPIRIT-remote).	No testable endpoints.	We will modify SPIRIT (in person) for people with mild AD and their surrogates and pretest it to assess acceptability.

OBJECTIVES	ENDPOINTS	JUSTIFICATION FOR ENDPOINTS
Aim 2		
In a 2-group RCT with 120 patient-surrogate dyads, evaluate the feasibility and acceptability of SPIRIT-remote and the preliminary efficacy compared to usual care (wait-list control) on preparedness outcomes for end-of-life decision making 2-3 days after the intervention	preparedness for EOL decision making: 1. Dyad congruence 2. Surrogate decision-making confidence (scale) 3. Surrogate preparedness scale	The primary goal of SPIRIT is to prepare the patient and surrogate for end-of-life decision making. The preparedness outcomes will indicate whether or to what extent SPIRIT accomplished the goal.
Exploratory		
Compare patient preparedness and patient and surrogate acceptability post-intervention and the completion of advance directives among the two treatment conditions at 1-year post-intervention	Patient preparedness scale, Patient acceptability and surrogate acceptability at 2-3 post-intervention Completion of an advance directive (binary)	
Using a qualitative method, in a sample of surrogates, explore their perceptions of the impact of SPIRIT at 1-year post-intervention.	No testable endpoints	We will interview a sample of surrogates at 1 year to assess the perceived impact of the intervention conditions.

[figure not shown]

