The most challenging aspects of designing this intervention trial are: a) determining an optimal follow-up time point and data collection mode to minimize the potential influence of patients' cognitive impairment on the outcome assessment, and b) maintaining blinding of data collectors. The first follow-up time point (Ideally 2-3 days post intervention however, consideration is given to difficulty of scheduling dyads and extension may result is to evaluate the impact of SPIRIT on preparedness outcomes while minimizing the potential influence of the patient's impaired ability to recall what was discussed during the SPIRIT session (i.e., the patient needs to recall what he/she clarified as goals-of-care preferences). We considered measuring the outcomes immediately following the intervention, but this would preclude blinding the data collector because of the modality difference. The second follow-up time (12 months post intervention) was chosen to help maximize the number of patients whose conditions progress to an advanced stage within the study period so that we can explore how surrogates experience having or not having an in-depth ACP discussion before the window of opportunity has closed. Although not ideal for people with mild AD, telephone-based data collection was chosen to assure blinding of data collectors and to reduce participants' travel burden. We have used phone-based data collection extensively in our previous studies with seriously ill patients and their surrogates using the procedures described above (see Post-Intervention Assessment).

As in our previous studies, we chose usual care as a comparison condition rather than an attention placebo control. In addition to the fact that there is no methodological standard for attention placebo controls in trials of psychosocial interventions,¹¹⁶ in the context of preparing for future medical care and end-of-life decision making, an attention placebo (information and discussion irrelevant to the context) would not meet the participants' expectations or motivation to participate in the study, and could cause a high refusal rate, dissatisfaction, and disproportional dropouts.¹¹⁶ We will offer SPIRIT-remote to control dyads at the completion of the 1 year follow-up if the patient has not progressed to moderate AD. The same protocol was used in our previous efficacy trial with 12-month follow-ups, and a wait-list control did not result in disproportional dropouts (SPIRIT [5.5%] vs usual care [2.0%]).³⁰

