Revised study design (V12):

In the effort to meet the target sample size, we expand study recruitment activities to 1) Georgia Memory Net sites (Augusta, Macon, Albany, and Columbus) in addition to Atlanta (Grady memory clinic serves as a memory assessment clinic for GA Memory Net), 2) Atlanta Regional Commission (ARC)/a federally designated Area Agency on Aging (AAA) serving older adults in 10 counties (Cherokee, Clayton, Cobb, DeKalb, Douglas, Fayette, Fulton, Gwinnett, Henry, and Rockdale), and 3) Alzheimer's Association's early stage program (e.g., early stage support groups, monthly lunch groups/Carpe Diem, High Museum tour groups, early memory loss support group series) and referrals to GA Memory Net that covers 33 counties.

Revised study design (V14):

Due to the coronavirus pandemic and social distancing recommendations from CDC, it is necessary to eliminate SPIRIT in-person modality to minimize in-person physical contacts with study participants. This makes the study a 2-group (SPIRIT-remote and usual care) RCT.

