6.2 PREPARATION/HANDLING/STORAGE/ACCOUNTABILITY

6.3 MEASURES TO MINIMIZE BIAS: RANDOMIZATION AND BLINDING

For Stage 1B pilot testing, [name] (statistician/Co-I) will generate a randomization scheme using stratified (by race, white vs non-white study site, Emory vs Grady), permuted block randomization with block size 6, using a random-number generator. Dyads will be randomized with equal allocation (1:1:1) to SPIRIT-in person, SPIRIT-remote, or usual care.

With Revision 14, randomization will be stratified by race (white vs non-white) within recruitment site (Emory, Rush, and Northwestern), with equal allocation to SPIRIT-in person or usual care.

Due to the nature of the intervention, blinding dyads to their group allocation is impossible, but the research staff assessing outcomes will be blind. Immediately after the completion of the baseline assessment by phone, the data collector will open a sealed envelope to identify group assignment and schedule an intervention session to take place ~2 weeks hence for SPIRIT- in person or –remote (with revision 14, all SPIRIT-remote), as well as a follow-up data collection session in the next 2-3 days.

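### The 44-46 surrogate interviews are counted from all 120 dyads but limited to the intervention group, which yields about 22-23 and leaves no usual-care surrogates for the planned comparison by treatment condition

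*Combined protocol and SAP*

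**What the plan says.** Section 8.1, under surrogates' perceived impact of SPIRIT, sets the population in its run-in heading and the number in the sentence that follows: "intervention group only). At 12 months, 44-46 surrogates will participate in a semi-structured interview by phone: approximately 26 surrogates of patients who have progressed". The number has two parts. The first is about 26 surrogates of patients who have progressed, based on a "22% progression rate". The second is a 20% random sample of surrogates whose patients have not progressed, given as about 18-20.

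Section 3 sets the trial size: "In a 2-group RCT with 120 patient-surrogate dyads". Section 4.2 (V14 revision) states the current structure: "This makes the study a 2-group (SPIRIT-remote and usual care) RCT". Section 6.3 sets the allocation under the same revision: "with equal allocation to SPIRIT-in person or usual care". That passage names the in-person arm where Section 4.2 names the remote arm. The label needs correcting, but the 1:1 ratio is clear.

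Two other passages depend on who is interviewed. Section 9.4.3 says: "To explore differences in themes by AD progression and by treatment condition, we will count the occurrence of themes". Section 4.2 explains that the 12-month time point was chosen to "explore how surrogates experience having or not having an in-depth ACP discussion before the window of opportunity has closed".

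**The concern.** The interview count and the restriction on who is interviewed do not fit together. If 26 and 18-20 were derived from the whole trial, an intervention-only sample cannot reach them by the stated rule.

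Two things are at stake. First, staff cannot tell from the protocol whether to select usual-care surrogates, or whether about 22 or about 45 interviews completes the aim. A faithful intervention-only execution would look like a 50% shortfall. Second, Section 9.4.3 plans a contrast by treatment condition. If only SPIRIT surrogates are interviewed, the usual-care side of that contrast is empty, and so is the group without the discussion that Section 4.2 relies on.

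**Working it through.** **Inputs**
- Dyads randomized: 120 (Section 3).
- Arms and allocation: two, 1:1 (Sections 4.2 and 6.3), so about 60 dyads receive SPIRIT. The 60 is an inference; the documents do not state it.
- Progression by 12 months: 22% (Section 8.1).
- Sampling fraction among those not progressed: 20% (Section 8.1).

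**Formula.** For N dyads in the sampled population:
- progressed = 0.22 × N
- sampled, not progressed = 0.20 × (N − 0.22 × N)
- interviews = the sum of the two

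**Step 1: reproduce the plan's figures with both arms, N = 120**
- 0.22 × 120 = 26.4 (plan: about 26)
- 0.20 × (120 − 26.4) = 0.20 × 93.6 = 18.7 (plan: about 18-20)
- Total 45.1 (plan: 44-46)

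All three stated numbers are recovered.

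**Step 2: apply the restriction as written, N = 60**
- 0.22 × 60 = 13.2
- 0.20 × (60 − 13.2) = 0.20 × 46.8 = 9.4
- Total 22.6, so about 22-23 interviews, none from usual care

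**Step 3: what would be needed to reach the stated numbers in one arm of 60**
- 26 progressed patients: 26 / 60 = 43.3% progression, about twice the planned 22%. At 22%, the binomial probability of 26 or more in 60 is 0.0002.
- 44-46 in total with 13 progressed: 31-33 of the other 47, a sampling fraction of 66-70% instead of 20%.
- 44 in total with the 20% fraction kept: 12 + 48p = 44 for progression rate p, so p = 67%.

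**Step 4: sensitivity of the intervention-only count**

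| Assumption | Progressed | Sampled, not progressed | Total |
|---|---|---|---|
| N = 60, 22% | 13.2 | 9.4 | 22.6 |
| N = 60, 10% (assumed) | 6.0 | 10.8 | 16.8 |
| N = 60, 30% (assumed) | 18.0 | 8.4 | 26.4 |
| N = 60, 22%, 3.8% dropout | 12.7 | 9.0 | 21.7 |
| N = 60, 22%, 5.5% dropout | 12.5 | 8.9 | 21.3 |
| N = 80, 22% | 17.6 | 12.5 | 30.1 |

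The dropout rates are those quoted from the previous efficacy trial: 3.8% overall (Section 5.5) and 5.5% in its SPIRIT arm (Section 4.2). N = 80 is two SPIRIT arms of 40, as in the superseded three-arm design. No row reaches 44.

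**The case against.** The best case for the plan has four parts.

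*The intervention group may exceed 60.* Dyads enrolled before V14 were allocated under the three-arm scheme or the V12 parallel designs, and their number is not given. If they count towards the 120, the intervention group could lie between 60 and 80. That would raise the yield to at most about 30 and lower the progression rate needed for 26 patients to 26 / 80 = 32.5%. This is a fair qualification, but 30 is still well short of 44, and Sections 3 and 9.2 describe the current trial as two-arm.

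*Treatment condition could mean in-person versus remote.* If any dyads received in-person SPIRIT before V14, that contrast exists within the intervention group. However, the documents give no count for it, the current design no longer plans it, and it would not supply usual-care surrogates. What is lost is specifically the comparison with usual care. The comparison by progression remains possible, with about 13 against 9 surrogates.

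*The restriction may be deliberate.* The aim in Sections 1.1 and 3 concerns perceptions of SPIRIT, and control dyads are offered it only after the 1-year follow-up, so they could not report its effect at 12 months. This is a sound reason to interview one arm. In that case the count and the text of Sections 9.4.3 and 4.2 are what must change.

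*The aim is minor.* Section 3 lists it as exploratory, while Sections 1.1 and 9.4.3 call it secondary. The analysis counts and graphs themes, with no test or power claim. This limits the importance of the point but does not remove the contradiction.

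**Conclusion.** The concern holds. The stated 44-46 interviews follow from the plan's own rates only when both arms are sampled (45.1 from 120 dyads). The restriction to the intervention group gives about 22-23, assuming 60 SPIRIT dyads and 22% progression. Allowing for the quoted dropout rates the figure is about 21-22, and the most generous count of SPIRIT dyads takes it to about 30. With no usual-care interviews, the theme comparison between SPIRIT and usual care has no data on one side, and the rationale for the 12-month time point is not met. The primary endpoints are unaffected. The point should be corrected because a stated size and a planned analysis are both wrong as written.

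**What to change.** Choose one of two routes and make Sections 8.1, 9.4.3 and 4.2 agree.

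1. **Sample both arms.** Remove the intervention-only restriction from Section 8.1. The 26, 18-20 and 44-46 then stand, with about 22-23 surrogates per arm (45.1 / 2 = 22.6), and the comparison by treatment condition is kept. The aim in Sections 1.1 and 3 and the heading in Section 8.1 should be widened beyond perceptions of SPIRIT. Section 8.1 should also state that usual-care surrogates are interviewed before their dyads are offered SPIRIT-remote, so that the experience of not having the discussion can still be observed.

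2. **Keep the restriction.** Restate the target in Section 8.1 as about 22-23 (about 13 progressed and 9 not progressed), with the assumed 60 SPIRIT dyads shown. Remove the comparison by treatment condition from Section 9.4.3, and reword the rationale in Section 4.2.

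Under either route, label the aim consistently as secondary or exploratory, and correct the arm name in Section 6.3.

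The cost is a protocol amendment with the IRB approval that the Statement of Compliance requires. Route 1 changes who is interviewed but needs no more than the 44-46 interviews already planned. Route 2 changes only text.
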